## **(2) Analysis step for completed datasets**

- For each of the 50 datasets the primary endpoint analysis of responder status will be based on an exact logistic regression model including fixed effects for treatment, region (Japan vs. non-Japan), and Baseline MMT-8 ( $\leq 142$  points vs.  $>142$  points).

## **(3) Pooling /combining step dataset**

- The corresponding results across the data sets are combined for overall inference using SAS® PROC MIANALYZE according to Rubin's rule to give the 1-sided p-value for hypothesis testing, the odds ratio (IgPro20 : placebo), and the corresponding 2-sided 95% confidence interval (CI). The primary endpoint analysis will utilize the mITT analysis set. Statistical significance will be assessed using a 1-sided alpha level of 0.025. The responder rate and corresponding 2-sided 95% CI will be estimated by treatment sequence. The primary endpoint analysis will also be provided for the subgroup of Japanese subjects.

Note: if a subject is erroneously assigned to the wrong baseline randomization stratum (eg, actual baseline MMT-8  $\leq 142$  points, but randomized in the stratum MMT-8  $> 142$  points) the analysis

---

will be done according to the actual stratum and not according to the stratum used for randomization. This applies to all analyses.

### 10.2.1 Sensitivity and Supplementary Analyses of Primary Endpoint

Sensitivity analyses of the primary efficacy endpoint will be performed to examine the robustness of the conclusion from the planned primary endpoint analysis to deviations from its underlying modelling assumptions and limitations in the data. All sensitivity analyses will be done based on the imputed TIS data used for the primary efficacy analysis and combined using Rubin's rule. Consistency of findings from the primary and sensitivity or supplementary analyses will be investigated and clinical plausibility of findings will be examined. Sensitivity analyses will address the following aspects:

- *(1) Standard Logistic Regression*

Regression model: standard logistic regression model will be fitted instead of exact logistic regression model. In case of non-convergence, the model will run without the fixed effects for region and MMT-8 stratification variable.

- *(2) Responder status of withdrawals not due to lack of efficacy or IMP related AEs based on last TIS values*

Sensitivity to the assumption that all early dropouts for reasons which are not related to the Ukraine war before Week 25 are non-responders will be assessed in this analysis. The responder status of subjects withdrawn from the study for reasons which are not related to the Ukraine war before Week 25 will be set to "responder" if:

- TIS is  $\geq 20$  points at the last study visit and at least at either of the previous 2 scheduled visits, and
- reason for withdrawal is not due to lack of efficacy, or IMP related AEs

- *(3) Responder status of withdrawals not due to lack of efficacy or death based on MI*

Sensitivity to the assumption that all early dropouts for reasons which are not related to the Ukraine war before Week 25 are non-responders will be assessed in this analysis.

- The responder status of subjects withdrawn from the study due to lack of efficacy or for subjects who die during study period 1 will be set to "non- responder"
- Data of all other subjects who are withdrawn from the study will be handled with the multiple imputation approach as described in Section 10.2.

- (4) *Exclusion of subjects dropping out due to the Ukraine war:*  
An additional sensitivity analysis will be done excluding subjects who drop out for reasons related to the Ukraine war using the same method as in Section 10.2.
- (5) *Responder status in subjects who have received increased oral corticosteroids without meeting DOW based on TIS results*

A supplementary analysis will address the following:

- (1) *Worsening of specific CSMs considered non-response – exclusion of subjects with dropping out due to the Ukraine war or subjects with missing TIS at Weeks 17 to 25*  
TIS with restrictions: individual CSMs are considered in addition to the TIS in the evaluation of responses at Week 17, Week 21, and Week 25. A subject should meet all of the following 3 criteria to be considered as showing response at each of the 3 study visits: TIS  $\geq$  20 points; no deterioration  $>$  absolute 10% from Baseline in MMT-8; and no deterioration  $>$  absolute 20% from Baseline in any other 2 CSMs. This analysis will exclude subjects who drop out for reasons related to the Ukraine war before Week 25 and thus will be based on an exact logistic regression model including fixed effects for treatment, region (Japan vs. non-Japan), and Baseline MMT-8 assessment ( $\leq$  142 points vs.  $>$  142 points). Subjects who completed Study Period 1 without the use of oral rescue corticosteroid treatment but have missing TIS values at Week 17, Week 21 or Week 25 will also be excluded from this analysis, except if response can be unambiguously determined by available data (eg, if TIS at Week 17 or Week 21 is missing but TIS at Week 25 is less than 20 points).

Note for clarification: a responder is defined as a subject with a response according to the above mentioned criteria at Week 25 and at least at 1 of the previous scheduled visits (Week 17 or Week 21) who completes 24 weeks of randomized IMP treatment without the use of oral rescue corticosteroid treatment.

- (2) *Threshold for TIS response in primary endpoint increased to 40*

The analytical approach in the sensitivity and supplementary analyses will be the same as in the primary endpoint analysis. These analyses will be based on the mITT and PP.

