### 10.4.2.3.2 Sensitivity and Supplementary Analyses of the Primary Efficacy Endpoint

Sensitivity analyses of the primary efficacy endpoint will be performed to examine the robustness of the conclusion from the planned primary endpoint analysis to deviations from its underlying modelling assumptions and limitations in the data. Consistency of findings from the primary and sensitivity or supplementary analyses will be investigated and clinical plausibility of findings will be examined.

The following sensitivity analyses will be done based on the imputed TIS data used for the primary efficacy analysis and combined using Rubin's rule. Sensitivity analyses will address the following aspects:

- Regression model: standard logistic regression model will be fitted instead of exact logistic regression model. In case of non-convergence, the model will run without the fixed effects for region and MMT-8 stratification variable.

- Reasons for withdrawal: sensitivity to the assumption that all early dropouts are non-responders will be assessed in this analysis. The responder status of subjects withdrawn from the study before Week 25 will be set to “responder” if:
  - TIS is  $\geq$  20 points at the last study visit and at least at either of the previous 2 scheduled visits, and
  - reason for withdrawal is not due to lack of efficacy, or IMP related AEs

An additional sensitivity analysis will be done excluding subjects who drop out for reasons related to the Ukraine war using an exact logistic regression model including fixed effects for treatment, region (Japan vs. non-Japan), and Baseline MMT-8 assessment ( $\leq$  142 points vs.  $>$  142 points).

A supplementary analyses will address the following:

- TIS with restrictions: individual CSMs are considered in addition to the TIS in the evaluation of responses at Week 17, Week 21, and Week 25. A subject should meet all of the following 3 criteria to be considered as showing response at each of the 3 study visits: TIS  $\geq$  20 points; no deterioration  $>$  absolute 10% from Baseline in MMT-8; and no deterioration  $>$  absolute 20% from Baseline in any other 2 CSMs. This analysis will exclude subjects who drop out for reasons related to the Ukraine war before Week 25 and thus will be based on an exact logistic regression model including fixed effects for treatment, region (Japan vs. non-Japan), and Baseline MMT-8 assessment ( $\leq$  142 points vs.  $>$  142 points).

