## 10.2 Analysis of Primary Endpoint

The primary endpoint is the responder status in each treatment sequence based on TIS assessments at Weeks 17, 21, and 25. Following the estimand described in Section 10.1, a responder is defined as a subject with a TIS  $\geq 20$  points at Week 25 and at least at 1 of the previous scheduled visits (Week 17 or Week 21) who completes 24 weeks of randomized IMP treatment without the use of oral rescue corticosteroid treatment.

Therefore, for subjects who do not withdraw from IMP or the study for reasons which are related to the Ukraine war before Week 25, non-responders will include subjects who meet any 1 of the following:

- TIS  $< 20$  points at Week 25
- TIS  $< 20$  points at both Weeks 17 and 21
- Withdraw from treatment or the study or receive oral rescue corticosteroid treatment before Week 25 (Note: for subjects with corticosteroid taper starting at Week 17, only an increase to doses greater than 125% of the Baseline corticosteroid dose following corticosteroid taper starting at Week 17 will be considered a “rescue” corticosteroid dose)

To ensure that the treatment effect is not confounded by the intercurrent event of premature withdrawal from IMP or the study due to the Ukraine war, the hypothetical strategy is applied for this intercurrent event to quantify the treatment effect in the absence of the Ukraine war [Meyer et al, 2020; Collins et al, 2020]. For subjects who withdraw from IMP or the study for reasons which are related to the Ukraine war before Week 25, scheduled TIS assessments after withdrawal are missing. These missing values can be considered missing at random (MAR) and multiple imputation will be used to derive the hypothetical post-intercurrent event TIS values and the corresponding response variables assuming that the subjects with missing TIS values continue in the same way as similar subjects in the study who did not withdraw prematurely. Multiple imputation is a simulation based approach where missing values are replaced by multiple Bayesian draws from the conditional distribution of missing data given the observed data and covariates, creating multiple completed data sets. The completed data sets can then be analyzed using standard methods. Note: If no TIS values are available for the subject for any post-randomization visit during Study Period 1, the subject will be excluded from the mITT analysis set (see Section 6).

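### Sensitivity analysis (2) of the primary endpoint has no rescue condition, so a rescued subject who leaves the study can count as a responder although the same subject completing Period 1 cannot

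*SAP*

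**What the plan says.** Under the primary rule in SAP 10.2, a subject is a non-responder on leaving treatment or the study for a non-war reason, or on having to "receive oral rescue corticosteroid treatment before Week 25". These are separate grounds. Protocol 5.3.1 adds that a rescued subject who stays in the study is classed as a non-responder at Week 25. The imputation step in SAP 10.2 adds every subject rescued in Period 1 to all 50 data sets as a non-responder.

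Sensitivity analysis (2) in SAP 10.2.1 gives its purpose as testing "Sensitivity to the assumption that all early dropouts for reasons which are not related to the Ukraine war before Week 25 are non-responders". It then resets "The responder status of subjects withdrawn from the study for reasons which are not related to the Ukraine war before Week 25" to responder on two conditions. The first is a TIS of at least 20 "points at the last study visit and at least at either of the previous 2 scheduled visits, and". The second is "reason for withdrawal is not due to lack of efficacy, or IMP related AEs". No further condition follows. Protocol 10.4.2.3.2 words its rule in the same way ("The responder status of subjects withdrawn from the study before Week 25 will be set to" responder), with the same two conditions and no mention of rescue.

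Sensitivity analysis (3) makes non-responders of subjects who leave for lack of efficacy or who die. For the remainder it states: "Data of all other subjects who are withdrawn from the study will be handled with the multiple imputation approach as described in Section 10.2".

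**The concern.** A sensitivity analysis is easiest to interpret when it changes one assumption. Analysis (2) is presented as a test of the dropout assumption, but for subjects with both events it also removes the rescue rule. Two subjects with identical rescue and identical TIS values up to Week 21 are then classified differently only because one of them left. The estimand in SAP 10.1 treats rescue as a treatment failure in its own right, whether or not the subject completes.

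What is at stake is how the robustness check is read. If (2) differs from the primary result, part of the difference could come from responses achieved after rescue steroid rather than from the handling of dropouts, and the output would not show which.

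**Working it through.** **Classification.** Take a subject rescued at Week 13 while on IMP, with TIS 25 at Weeks 17 and 21, both on IMP. Apply the rules as written:

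| Subject | Primary rule | (2) as written | (2) with a no-rescue condition |
|---|---|---|---|
| Rescued, completes Period 1 | non-responder | non-responder | non-responder |
| Rescued, leaves after Week 21 for another reason | non-responder | **responder** | non-responder |
| Not rescued, leaves after Week 21 for another reason | non-responder | responder | responder |

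The second row is the anomaly. The third shows that the added condition leaves the intended relaxation intact.

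**Can rescue and a TIS of 20 or more coexist?** Yes. Rescue is allowed from Week 9 and the subject continues IMP (protocol 5.3.1), so TIS may reach 20 afterwards. They can also coincide at one visit. DOW can be met on the extramuscular VAS alone, while SAP Table 5 gives 7.5 (physician global, over 5%) + 10 (MMT-8, over 2%) + 2.5 (patient global, over 5%) = 20.

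**Planned rates.** With SAP Table 3 and a 0.9 chance of keeping a response, the responder probability is p17 × (0.9² + 0.1 × q) + (1 − p17) × q × 0.9, where q is the chance of gaining a response:
- IgPro20: 0.65 × (0.81 + 0.02) + 0.35 × 0.2 × 0.9 = 0.6025
- Placebo: 0.30 × (0.81 + 0.01) + 0.70 × 0.1 × 0.9 = 0.3090

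Full enumeration of the 1-sided Fisher test at 63 per arm gives power 0.9037, against 0.905 in SAP Table 14. That table's median rates (0.603 and 0.317) correspond to 38 and 20 responders out of 63.

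**Number affected.** The documents give no rescue or dropout rates. Assume that 5–15% are rescued, that 10–20% of these leave for another reason, and that 30–60% of those leavers have qualifying TIS values:
- low: 63 × 0.05 × 0.10 × 0.30 = 0.1 per arm
- high: 63 × 0.15 × 0.20 × 0.60 = 1.1 per arm

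Each such subject moves an arm's rate by 1/63 = 1.6 points.

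**Effect of one subject (1-sided Fisher, 63 per arm, level 0.025).** Fisher's test stands in here for the pooled exact logistic regression.

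| Before (IgPro20 v placebo) | p | After one reset | p |
|---|---|---|---|
| 38 v 20 | 0.0011 | 38 v 21 | 0.00205 |
| 32 v 20 | 0.0230 | 32 v 21 | 0.0353 |
| 31 v 20 | 0.0345 | 32 v 20 | 0.0230 |

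At about the planned rates one subject changes nothing of substance. At the boundary one subject can move the result across 0.025 in either direction.

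**The case against.** The best reply is that the primary rescue rule carries over without being restated. SAP 10.2.1 closes by saying that these analyses follow the primary analytical approach, and the protocol equivalent allows for exceptions only where stated. SAP 14.1.1 treats a rescued subject as showing no response from that visit on. Increased steroid use without DOW has its own analysis, (5). This is good evidence of what was intended. It does not settle what would be programmed, because (2) expressly rewrites responder status for leavers and lists its conditions in full. SAP 14.1.1 also says the same of withdrawal, which (2) plainly overrides. Supplementary analysis (1), by contrast, does write out the no-rescue requirement.

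A second reply stands in part. Under SAP 8.2.3 and the footnote to Table 8, assessments after IMP discontinuation are used only within 7 days and only if no rescue preceded them. A rescued subject's TIS from a withdrawal visit after stopping IMP is therefore excluded. A reader might infer that every rescued leaver is reset, but the documents do not support that. The gap is confined to subjects whose qualifying visits were on IMP, such as one lost after Week 21.

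A reader might also infer that analysis (3) has the same fault, since "Data of all other subjects who are withdrawn from the study will be handled with the multiple imputation approach" contains no rescue exception. It does not. The approach cited there is that of Section 10.2, which imputes alongside completers who had no rescue and adds rescued subjects back as non-responders.

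Finally, extra placebo responders would make (2) harder to pass, so the gap does not systematically flatter the product. That is correct.

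**Conclusion.** The point holds for analysis (2) and its protocol counterpart, as a minor one. As written, the rule gives a rescued leaver a better outcome than an otherwise identical rescued completer, contrary to the analysis's own stated purpose.

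The estimate of 0.1 to 1.1 subjects per arm rests wholly on the assumed rates. It takes no account of the 7-day rule, so if anything it is too high for those rates. Protocol 3.3.1 itself expects few subjects to meet DOW. The direction depends on which arm the affected subjects are in. A reader might go further and see a threat to the trial's main conclusion. The documents do not support that: the primary analysis, the alpha level and the sample size do not depend on (2).

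**What to change.** In SAP 10.2.1, add a third condition to analysis (2): and no oral rescue corticosteroid treatment was received before withdrawal. The protocol 10.4.2.3.2 wording should match. Because the protocol leaves the full description of methods to the SAP, a SAP clarification could come first and the protocol be aligned at the next amendment. If resetting rescued leavers is in fact intended, the SAP should say so and explain why they differ from rescued completers.

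Analysis (3) needs no correction. A cross-reference noting that rescued subjects stay non-responders under Section 10.2 is optional.

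The cost is one clause and one line of code. SAP Section 3 requires decisions on the primary data analysis before unblinding, so the clause should be in place by then.

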### 10.2.2 Subgroup Analyses of Primary Endpoint

Internal consistency of observed treatment effect across major subgroups on the primary endpoint will be investigated as part of exploratory analyses. Subgroup factors are shown in the list below:

- Age: < 65 years,  $\geq$  65 years
- Age at initial diagnosis of DM: < 18 years,  $\geq$  18 to < 40 years,  $\geq$  40 years
- Gender: Female, Male
- Baseline MMT-8: MMT-8  $\leq$  142 points, MMT-8  $>$  142 points  
Note: if a subject is erroneously assigned to the wrong baseline randomization stratum (eg, actual baseline MMT-8  $\leq$  142 points, but randomized in the stratum  $>$  142 points) the analysis will be done according to the actual stratum and not according to the stratum used for randomization. This applies to all analyses.
- Region (1): Japan, non-Japan
- Region (2): USA, non-USA
- Disease severity:
  - Mild (Physician Global Disease Activity VAS  $\geq$  2 cm and  $<$  4.5 cm)
  - Moderate (Physician Global Disease Activity VAS  $\geq$  4.5 cm and  $<$  7.5 cm)
  - Severe (Physician Global Disease Activity VAS  $\geq$  7.5 cm)

Subgroup analysis will use the same analytical approach as in the primary endpoint analysis. For each of the imputed data sets the analysis of responder status will be based on an exact logistic regression model including fixed effects for treatment, region (Japan vs. non-Japan), and Baseline MMT-8 ( $\leq$  142 points vs.  $>$  142 points) and the corresponding results across the imputed data sets are combined for overall inference using Rubin's rule. The test results will be summarized for each level of subgroup, including at least the following: the number of subjects by treatment, the number (%) of responders by treatment, 95% CI for % of responders by treatment; odds ratio with 95% exact CI and one-sided p-value. A forest plot of subgroups with odds ratio and 95% CI displayed for each level of subgroup will be provided.

### 10.3 Key Secondary Estimand

The key secondary interest is to quantify the treatment effect of IgPro20 under the hypothetical situation where no subjects receive oral rescue corticosteroid treatment or withdraw from treatment or the study before Week 25.

The key secondary estimands in line with the key secondary interest of the study are described as follows for the continuous key secondary endpoints:

- Population: the target patient population defined by eligibility criteria and who received any amount of randomized IMP treatment and have post baseline efficacy results in Study Period 1 (mITT). For details see Section 6.
- Variables: TIS, changes from Baseline in MMT-8, and changes from Baseline in CDASI total activity score at Week 25
- Intercurrent event: when a subject withdraws from randomized IMP treatment or receives oral rescue corticosteroid treatment before Week 25, data after withdrawal or oral rescue will be considered missing for the continuous endpoints, even if data are collected in the study
- Population-level summary: mean of the variables by treatment sequence

The key secondary estimand for the binary key secondary endpoint reduction of oral concomitant corticosteroid dose by at least 25% at Week 25 is described as follows:

- Population: the target patient population defined by eligibility criteria and who received any amount of randomized IMP treatment and have post baseline efficacy results in Study Period 1 (mITT). For details see Section 6.
- Variables: reduction of oral concomitant corticosteroid dose at Week 25
- Intercurrent events:
  - withdrawal from randomized IMP or the study, which is not related to the Ukraine war, or receiving oral rescue corticosteroid treatment before Week 25: data after withdrawal or oral rescue will be considered no reduction of oral concomitant corticosteroid even if data are collected in the study
  - withdrawal from randomized IMP or the study which is related to the Ukraine war will be addressed using the hypothetical strategy.
- Population-level summary: percentage of subjects who are able to reduce the oral concomitant corticosteroid dose by at least 25% by treatment sequence

## 10.4 Analysis of Key Secondary Endpoints

The following key secondary efficacy endpoints are defined:

- TIS at Week 25
- Changes from Baseline MMT-8 at Week 25
- Changes from Baseline CDASI total activity score at Week 25
- Reduction of oral concomitant corticosteroid dose by at least 25% at Week 25

Each of the following 3 key secondary efficacy endpoints will be analyzed separately using the MMRM. The terms to be included in the model for each key secondary endpoint are as follows:

- TIS at Week 25: treatment, visit, the interaction between treatment and visit, region, and Baseline MMT-8 stratification variable ( $\leq 142$  points vs.  $> 142$  points) as fixed effects, subjects as a random effect;
- Changes from Baseline MMT-8 at Week 25: treatment, visit, the interaction between treatment and visit, and region as fixed effects, Baseline MMT-8 as a continuous covariate, subjects as a random effect;
- Changes from Baseline CDASI total activity score at Week 25: treatment, visit, the interaction between treatment and visit, region, and Baseline MMT-8 stratification variable ( $\leq 142$  points vs.  $> 142$  points) as fixed effects, Baseline CDASI total activity score as a continuous covariate, subjects as a random effect.

Analyses will start with the unstructured covariance matrix; compound symmetry will be adopted in case of convergence difficulties. The differences between treatment sequences, the corresponding 95% CIs, and 1-sided p-values from the models will be provided. Point estimates for the average values in each treatment group will also be presented along with their standard errors.

Only data collected up to the end of Period 1 will be included in the MMRM analysis. For subjects who receive oral rescue corticosteroid treatment or who withdraw from treatment or the study, data after the first administration of oral rescue corticosteroid treatment or withdrawal from randomized IMP treatment will be considered missing and thus not included in the MMRM analysis.

The analysis of the fourth key secondary endpoint, ie, the proportion of subjects who are able to reduce the oral concomitant corticosteroid dose by at least 25% at Week 25 will be done in analogy to the analysis of the primary endpoint, see Section 10.2. The oral concomitant corticosteroid dose at Week 25 will be considered to be reduced by at least 25% when the

---

average daily dose of Week 24 is reduced by at least 25%, as treatment with IgPro20 starts in both treatment sequences on the first day of Week 25.

For subjects who do withdraw from IMP or the study for reasons which are related to the Ukraine war before Week 25, the resulting missing values can be considered missing at random (MAR) and multiple imputation will be used to derive the hypothetical post-intervent event reduction of oral concomitant corticosteroid dose in percent (%reduction). Replacement of trailing missing %reduction values for weeks 17 to Week 24 (ie, monotone missings) will be done if the subject received oral corticosteroid medication at baseline using multiple imputations based on monotone regression with the covariates treatment, country, and Baseline MMT-8 ( $\leq$  142 points vs.  $>142$  points), baseline oral corticosteroid dose and %reduction values from previous weeks starting at Week 17 (50 imputations) by SAS® PROC MI. Note: If the subject did not receive any oral corticosteroid medication at baseline %reduction will be set to 0. The multiple imputation process will correspond to the one for the primary endpoint described in Section 10.2. A subject is considered a responder regarding this endpoint, if he/she is able to reduce the oral concomitant corticosteroid dose by at least 25% at Week 24, ie if %reduction is  $\geq 25$ .

For each of the 50 data sets resulting from the multiple imputation process the analysis of the 4th key secondary endpoint will be based on an exact logistic regression model including fixed effects for treatment, region (Japan vs. non-Japan), and Baseline MMT-8 ( $\leq$  142 points vs.  $>142$  points). The corresponding results across the data sets are combined for overall inference using SAS® PROC MIANALYZE according to Rubin's rule.

The 4 key secondary endpoints will be analyzed with an overall 1-sided alpha level of 0.025. The hypotheses associated with the key secondary endpoints will be formally tested and therefore adjusted for multiplicity. The key secondary analyses will be performed based on the mITT and repeated for the PP.

